2. STUDY OBJECTIVES

The objectives of the study are:

2.1 *Primary objective*

The primary objective of the study is to investigate the efficacy, as measured by objective response rate (ORR) and overall survival (OS), of rovalpituzumab tesirine as third-line and later treatment for subjects with relapsed or refractory delta-like protein 3 (DLL3)-expressing small cell lung cancer (SCLC).

2.2 *Secondary objectives*

- To assess duration of response (DOR), clinical benefit rate (CBR) and progression-free survival (PFS) in subjects with relapsed or refractory DLL3-expressing SCLC treated with rovalpituzumab tesirine

- To assess the safety and tolerability of rovalpituzumab tesirine
- To characterize the pharmacokinetics of rovalpituzumab tesirine and incidence of anti-therapeutic antibodies (ATA)

2.3 *Exploratory objectives*

- To explore relationship of DLL3 expression to clinical outcome during treatment with rovalpituzumab tesirine
- To explore the efficacy and safety of rovalpituzumab tesirine retreatment when administered to subjects with DLL3-expressing SCLC who previously achieved clinical benefit on rovalpituzumab tesirine
- To explore the effect of rovalpituzumab tesirine on disease biomarkers and pharmacodynamics

3. STUDY DESIGN

3.1 *General Description*

This is an open-label, single-arm, Phase 2 study of rovalpituzumab tesirine in DLL3-expressing SCLC subjects with relapsed or refractory disease after receiving at least 2 previous regimens, including at least one platinum-based regimen. Only subjects with tumor cell expression that is DLL3 positive based on an immunohistochemistry (IHC) assay specification (Ventana mouse assay, SCRX16.65) will be enrolled in the study.

3.2 *Determination of Sample Size*

3.3 Methods of Assigning Subjects to Treatment and Stratification

SCRX001-002 is a Phase II open-label, single-arm, non-comparative, multicenter study of rovalpituzumab tesirine in DLL3-expressing SCLC subjects with relapsed or refractory disease after receiving at least 2 previous regimens, including one platinum-based regimen. Subjects will be screened and identified as eligible for the study by the Investigator at each site. Once screening procedures have been completed for the subject, the Registration and Enrollment Form will be completed and submitted to the sponsor or designee to confirm eligibility. Eligible subjects will be registered to the study centrally by the CRO, PPD.

No stratification is required.

4. STUDY ENDPOINTS AND COVARIATES

A large black rectangular redaction box covering the majority of the page content below the section header.

4.1 Demographic and Baseline Characteristics

- Demography includes: Age at baseline (years), sex, ethnicity, race, weight at baseline (kg), height (cm) and countries/sites
- Baseline Characteristics include: ECOG Performance Status at baseline, history of brain metastases, presence of brain metastases at baseline, baseline tumor burden, smoking history status and pack years of smoking for previous and current smokers, renal function at baseline, and hepatic function at baseline
- Disease History: stage at initial diagnosis, stage at study entry, history of paraneoplastic syndrome, number of metastatic sites, sites of metastatic disease, and time from initial diagnosis to first dose (months)
- Prior therapy information include:
 - Prior lines of systemic therapy (2, 3, 4 or more)
 - Response to frontline therapy (sensitive, refractory, resistant)
 - Prior systemic therapies drug categories
 - Best overall response of prior systemic therapies
 - Time from diagnosis to the last progression (months)
 - Time to progression on second line (2L) therapy
 - Prior Radiation Therapy (Yes, No) and number of radiation sites (0, 1, 2, 3 or more)
 - Prior Cancer Surgery (Yes, No) and number of surgeries (0, 1, 2, 3 or more)
- Medical History

4.2 DLL3 Expression

[REDACTED]
[REDACTED]
All patients enrolled in the TRINITY study are
DLL3 positive by [REDACTED]

[REDACTED]

[REDACTED]

If multiple scores are available for a subject, then the score with the latest sample date is used. If there are multiple scores available at the latest date then the highest value is used.

4.3 Primary Efficacy Endpoint

This study has two primary endpoints:

- Objective response rate (ORR) through the initial treatment period
- Overall survival (OS)

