This study has two co-primary endpoints:

- Objective response rate through the End of Treatment (42 ± 3 days after last dose) for DLL3 high and for DLL3 positive, per IHC assay specification subjects
- Overall survival for DLL3 high and for DLL3 positive, per IHC assay specification subjects

Secondary:

- Duration of response for DLL3 high and for DLL3 positive subjects, per IHC assay specification
- Clinical Benefit Rate for DLL3 high and for DLL3 positive subjects, per IHC assay specification
- Progression-free survival for DLL3 high and for DLL3 positive subjects, per IHC assay specification

Safety Endpoints

Safety assessments include vital signs, body weight, ECOG score, clinical adverse events, laboratory tests (hematology, serum chemistries, urinalysis, and coagulation), ECGs, echocardiogram, fluid retention questionnaire, and monitoring of concomitant therapies.

Pharmacokinetic and Pharmacodynamic Endpoints

Pharmacokinetic assessments will include blood samples for rovalpituzumab tesirine and anti-therapeutic antibodies (ATAs).

Pharmacodynamic and biomarker assessments will include analyses of tumor tissue for DLL3 expression, and of blood samples for tumor markers, [REDACTED] and soluble biomarkers such as soluble DLL3.

STATISTICAL METHODS:

Sample Size

A response rate of 15% or less is typically observed in this advanced state of the disease. It is assumed that at least 25% of subjects treated with rovalpituzumab tesirine will achieve complete or partial response. In Stage 1, up to 60 evaluable, DLL3 high (per IHC assay specification), subjects may be enrolled. In Stage 2, at least 63 additional subjects that are DLL3 high (per IHC assay specification) will be enrolled, to maintain an 80% power at a one-side significance level of 0.025. The number of subjects evaluated at each stage and the minimum

number of responders to continue from Stage 1 to Stage 2 were estimated using the minimax principle of the Simon two-stage design.

Up to approximately 123 DLL3 high, third-line subjects will be enrolled. The total sample size for this study will be determined by the proportion of enrolled subjects with DLL3 high expression among those who are DLL3 positive.

Efficacy Analysis

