2.2 Endpoints

2.2.1 Primary Efficacy Endpoints

This study has two primary endpoints:

- Objective response rate through the End of Treatment (42 ± 3 days after last dose) for DLL3 high and for DLL3 positive subjects, per IHC assay specification
- Overall survival for DLL3 high and for DLL3 positive subjects, per IHC assay specification

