9.2 Statistical and Analytical Plans

The statistical and analytical plans presented below summarize the more complete plans to be detailed in the statistical analysis plan (SAP). A change to the data analysis methods described in the protocol will require a protocol amendment only if it alters a principal feature of the protocol. The SAP will be finalized prior to database lock. Any changes to the methods described in the final SAP will be described and justified in the clinical study report.

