9.2.6.1.1 Objective Response Rate

The objective response rate defined as the proportion of subjects whose best overall response is either complete response (CR) or partial response (PR) according to RECIST version 1.1. The best overall response is the highest recorded response through end of treatment (42 ± 3 days after last dose).

The objective response rate will be estimated based on the maximum likelihood estimator (i.e., crude proportion of subjects with best overall response of CR or PR). The estimate will be accompanied by a two-sided exact 95% binomial confidence interval (CI).

A supplemental analysis of ORR will be performed based on assessments by the Investigator.

Objective response rate following retreatment with rovalpituzumab tesirine will be reported separately as a secondary, supplemental analysis.

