6. ANALYTIC DEFINITIONS

Initial Treatment Period includes all assessments prior to the retreatment period or the start of new anti-cancer therapy, whichever occurs earlier. For subjects who will not be retreated, the initial treatment period will include assessments till the start of new anti-cancer therapy or the end of study, whichever occurs earlier.

Baseline Evaluation is the last available evaluation prior to receiving first dose of study drug. This will include any unscheduled evaluation prior to first dose. For subjects receiving retreatment, baseline for that period is the last available evaluation prior to receiving first dose of study drug for retreatment.

Change from Baseline is defined as the difference between the baseline value as defined above and the value at the respective time point. Negative values represent decreases from baseline; positive values will reflect increases from baseline.

Percent Change from Baseline is defined as the change from baseline divided by the baseline value times 100%. That is

$$100x (\text{Post-baseline value} - \text{baseline value}) / (\text{baseline value}).$$

Age at Baseline (in years) is defined from date of birth to date of first dose.

Last Evaluable Disease Assessment, for purpose of censoring, will be the last assessment with a response that is determined to be CR, PR, SD, PD, or Not Evaluable (NE).

Treatment-Emergent Adverse Event during this period is defined as any adverse event occurring on or after initiation of therapy and prior to the earlier of the start of retreatment period for those received Rova-T retreatment and the start of a subsequent anti-cancer therapy. Any adverse event with onset on or after the first dose of retreatment till the start of the next retreatment period or the start of a subsequent anti-cancer therapy will be considered treatment-emergent for that retreatment period.

Concomitant Medication is defined as a medication or treatment other than the study drug is considered concomitant if it is taken at any time on or after the first dose date. A medication taken prior to first dose date and continuing past first dose date is considered concomitant. Concomitant medications that stopped prior to first dose of retreatment will only be included in the initial treatment period. Medications started after the first of retreatment will be considered concomitant during the retreatment period.

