7.5.1 Objective Response Rate

Overall Response at each visit post-baseline is assessed based on a subject's lesion measurements or assessments. Overall Response is assessed as CR, PR, SD, PD, or NE as defined by RECIST version 1.1. An additional category of Early Death will also be included which is defined as subjects who died prior to any post-baseline response assessment. Amongst all the Overall Responses, the best Overall Response is then determined. The best Overall Response will be ordered as CR, PR, SD, PD, or NE; with CR being the best. A subject will be considered to have a best overall response of SD if there is a minimum interval of 42 days between the date of assessment and (-7 days to allow for scheduled visit window per the protocol) the first dose date. Subjects who died prior to the first post-baseline lesion assessment are included in the Early Death category. The Not Evaluable (NE) category includes subjects who are not evaluable as indicated by the IRC or by the Investigator, in analyses of overall response per IRC and investigator, respectively. Subjects who discontinued the study prior to obtaining a post-baseline scan for lesion assessment will be categorized as Indeterminate.

Objective Response is defined as a subject with the best Overall Response of Complete Response (CR) or Partial Response (PR) prior to receiving any subsequent anticancer therapy and retreatment, and is confirmed by a consecutive response assessment at least 4 (28 days) from the initial determination of CR/PR per RECIST v 1.1 as described in Table 1:

Table 1 – Confirmed partial and complete response

Overall response First time point	Overall response Subsequent time point	BEST overall response
CR	CR	CR
CR	PR	SD, PD or PR ^a
CR	SD	SD (if minimum duration for SD met), otherwise, PD
CR	PD	SD (if minimum duration for SD met), otherwise, PD

CR	NE	SD (if minimum duration for SD met), otherwise, NE
PR	CR	PR
PR	PR	PR
PR	SD	SD
PR	PD	SD (if minimum duration for SD met), otherwise, PD
PR	NE	SD (if minimum duration for SD met), otherwise, NE
NE	NE	NE

Note: In case of SD, measurements must have met the SD criteria at least once after study entry at a minimum interval of 42 days (-7 days to allow for scheduled visit window per the protocol).

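### The SAP counts primary objective responses beyond End of Treatment, where the protocol closes the window, and its visible text plans no ORR limited to End of Treatment

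*SAP*

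**What the plan says.** Protocol 2.2.1 gives the first primary endpoint as "Objective response rate through the End of Treatment (42 ± 3 days after last dose"), for DLL3 high and for DLL3 positive subjects. Protocol 9.2.6.1.1 repeats the limit in the analysis definition: "The best overall response is the highest recorded response through end of treatment (42 ± 3 days after last dose"). The synopsis and Protocol 3.1 tie the endpoint to the same assessment. The ORR definition mentions no confirming scan.

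The SAP states that it implements Protocol Version 4.0. SAP 4.3 gives the endpoint as "Objective response rate (ORR) through the initial treatment period". SAP 6 ends that period at retreatment or new anti-cancer therapy; for subjects who are not retreated, "the initial treatment period will include assessments till the start of new anti-cancer therapy or the end of study, whichever occurs earlier". SAP 9 brings every scan, scheduled or not, into the response analyses. SAP 7.5.1 adds that an objective response counts only if it "is confirmed by a consecutive response assessment at least 4 (28 days) from the initial determination of CR/PR".

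Protocol 9.2 leaves detail to the SAP, but says that a change of analysis method "will require a protocol amendment only if it alters a principal feature of the protocol".

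**The concern.** The two documents define the primary ORR over different periods. A subject whose first CR or PR appears on a follow-up scan is a non-responder under the protocol and can be a responder under the SAP. If the SAP is followed as it reads, the reported primary figure answers a different question from the one the protocol poses, and nothing in the visible text explains why.

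This matters because ORR is the endpoint on which the two-stage design rests. The synopsis sets the reference rate ("A response rate of 15% or less is typically observed in this advanced state of the disease") against the target ("It is assumed that at least 25% of subjects treated with rovalpituzumab tesirine will achieve complete or partial response"), a gap of 10 percentage points. Neither rate is tied to a window or a confirmation rule, so the definition used at the analysis decides what is compared with them.

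**Working it through.** **1. When the protocol window closes.** Dosing is on Day 1 of two 6-week cycles, so dose 2 falls on Day 1 + 42 = Day 43. EOT is 42 ± 3 days later: Day 85, range Day 82 to 88. The ± 2-day window for dose 2 widens this to Day 80 to 90. Two disease assessments are scheduled by then: one in the 7 days before dose 2 and one at EOT.

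**2. What the SAP window adds.** Protocol 6.5 schedules follow-up scans every 6 weeks until 6 months, then every 12 weeks. Under Protocol 3.1 and note 21 of the schedule, imaging continues only until progression or new anti-cancer treatment. The extra exposure is therefore follow-up scans in subjects who are still progression-free.

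**3. Whether any planned rate stops at EOT.**

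| Analysis in the visible SAP | Confirmation | Window ends at |
|---|---|---|
| ORR by central review or investigator (7.5.1) | At least 28 days later | Retreatment, new therapy or end of study |
| Unconfirmed CR/PR rate, either reader (4.4, 7.5.1) | None | Same |
| Table 14.2_1.2.2, best response by line of therapy and onset (Appendix G) | Not stated | Onset categories not defined |

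None is limited to EOT.

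**4. Direction.** With the confirmation rule held fixed, lengthening the window can only add responders. With the window held fixed, requiring confirmation can only remove them. The two changes oppose each other, and the documents give neither the share of responses first seen after EOT nor the share left unconfirmed.

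**5. Size per subject.** At 123 subjects, 1/123 = 0.81 percentage points. The SAP's primary sets are all treated DLL3 high and all treated DLL3 positive subjects, including fourth-line and later. If these exceed 123, each subject moves ORR by less.

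**6. What a shift would mean for the design (illustration).** Inputs from the synopsis: 15% against 25%, one-sided 0.025, 80% power, 60 + 63 = 123 subjects, continue if more than 9 of 60 respond. The final cut-off is not visible, since Protocol 9.1 is redacted, so it is derived here. With X1 responders in stage 1 and X in total, the chance of passing is the sum over x > 9 of P(X1 = x) × P(stage 2 responders > r − x).

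| r (pass if X > r) | At 15% | At 25% |
|---|---|---|
| 25 | 0.0398 | 0.8488 |
| 26 | 0.0242 | 0.8001 |
| 27 | 0.0141 | 0.7403 |

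Of these, only r = 26 meets both stated targets, so the planned size reproduces. With r = 26:

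- If the true through-EOT rate is 15% and later scans add an assumed 1, 2, 3 or 5 points, the chance of passing rises from 2.4% to 4.9%, 9.0%, 14.8% or 31.9%.
- If the true unconfirmed rate is 25% and an assumed 10%, 20% or 30% of responses are not confirmed (rates 22.5%, 20.0%, 17.5%), it falls from 80.0% to 58.1%, 31.9% or 11.7%.

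The planned analysis is an estimate with an exact 95% interval, so these figures show sensitivity; they are not error rates of the reported analysis.

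**The case against.** The best defence is that the SAP is meant to be the fuller document and may be spelling out what the protocol intended. For confirmation this has real force. Protocol 9.2.6.2.1 measures duration of response from a CR or PR that is later confirmed, 9.2.6.2.2 uses similar wording, and the SAP ties its rule to RECIST 1.1, the criteria the protocol names for ORR. A reader might infer that the SAP reversed a protocol decision not to confirm. The documents do not support that: the ORR definition is silent, and silence is not a decision.

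The defence does not reach the window. The protocol states the EOT limit repeatedly, and the SAP's period is a different one.

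A reader might also infer that the protocol's endpoint is estimated nowhere. That cannot be shown. SAP 3.2 and parts of SAP 4 and 5.1 are redacted, and Table 14.2_1.2.2 may split responses by timing. The claim is limited to the visible text.

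Nor do the two rules contradict each other as written. A confirmed response inside a window closed at EOT would be unreachable when CR or PR is first seen on the EOT scan, but neither document states that combination; the SAP allows confirming scans after EOT. It would also be too strong to say that a one-dose subject could never have a confirmed response by EOT. Protocol 6.4 places the EOT visit at the later of 42 ± 3 days after the last dose and 7 days after the documented decision to stop, dose interruptions of up to 6 weeks are allowed, and unscheduled scans count.

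Finally, late first responders may be few, because they must still be progression-free at about week 12 in a disease for which Protocol 1.1.1 gives a median survival below 6 months after recurrence. That is plausible, but the documents give no figure.

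**Conclusion.** The window mismatch is in the current text of both documents and is enough by itself to need correction. The confirmation difference is secondary: it should be stated identically in both places, but it may only be detail that the protocol left out.

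One might conclude that the SAP inflates ORR, or that it deflates it. Neither follows, because the two changes act in opposite directions and the documents give the size of neither. What can be said is that each reclassified subject is worth at most about 0.8 points, assuming at least 123 subjects in the analysis set, and that the pass probabilities above rest on assumed shifts and a derived cut-off of 26. The consequence is an unclear primary estimand, not a demonstrated bias.

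**What to change.** In SAP 4.3 and 7.5.1, add an ORR limited to CR or PR first recorded on or before the initial-course EOT assessment. Report it in two forms: without confirmation, which is the protocol definition as written, and with confirmation, allowing the confirming scan after EOT. With on-time dosing the next follow-up scan falls 12 weeks ± 1 week after dose 2 (Day 43 + 84 = Day 127, range 120 to 134). That is at least 120 − 88 = 32 days after EOT, so the 28-day interval fits the existing schedule. Make the EOT-limited rate primary, say which of its two forms is primary, and keep the whole-period rate as supportive.

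If the longer window is what is wanted, amend Protocol 2.2.1 and 9.2.6.1.1 to it, since the primary endpoint's definition is a principal feature under Protocol 9.2. Then keep the through-EOT rate as a named supportive analysis.

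Either way, state one confirmation rule in the same words in both documents. Say whether EOT for this purpose means the 42 ± 3 day window or the visit as dated in Protocol 6.4, and define the onset categories of Table 14.2_1.2.2.

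The cost is wording, one derived onset flag and one or two table rows from data already collected, plus a protocol amendment under the second route. If the EOT-limited rate becomes primary, the reported figure may be slightly lower, because late-onset responses move to a supportive row.

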4.4 Secondary Efficacy Endpoints

- Best Overall Response of CR or PR Rate
- Clinical benefit rate (CBR)
- Duration of Response (DOR)
- Progression-free Survival (PFS)

4.5 Safety Endpoints

- Adverse Events
- Vital signs
- Laboratory abnormalities
- Electrocardiographic intervals (e.g. QTc)
- Echocardiography

- Components of a fluid retention questionnaire

The fluid retention questionnaire serves as a tool for patient management on site.

Data from the questionnaire will not be entered into the EDC and will not be analyzed.

4.6 Pharmacokinetic Pharmacodynamic, and Biomarker Endpoints

Pharmacokinetic Endpoints

- Specific pharmacokinetic parameters of rovalpituzumab tesirine (e.g. C_{max} , AUC)
- Anti-therapeutic antibodies against rovalpituzumab tesirine

Pharmacodynamic and Biomarker Endpoints

- Tumor DLL3 expression
- Inflammatory Markers
- Blood Tumor Markers
- Biomarkers, including soluble DLL3

Analyses of DLL3

expression and other biomarkers for the purpose of the Clinical Study Report are outlined in Section 7.7 of this document.

5. ANALYSIS POPULATIONS AND SUBGROUP

Analyses of ORR, DOR, CBR, DOCB, and PFS will be performed using response assessments by IRC, and by investigators.

5.1 Analysis Population

The modified intent-to-treat (ITT) population includes all subjects who received any amount of study drug. The modified ITT population is the same as the safety analysis population. The modified ITT population is the primary analysis population for efficacy,

unless otherwise specified, and efficacy analyses will be performed in the following analysis sets:

- All DLL3 High subjects in the modified ITT population
- All DLL3 Positive subjects in the modified ITT population

In addition, efficacy analyses will be performed for the modified ITT population regardless DLL3 status. [REDACTED]

The efficacy-evaluable population includes subjects in the modified ITT who had at least one post-baseline response assessment, or those that did not have a post-baseline response assessment and died within 42 days due to underlying disease progression. Analyses based on investigator responses will include subjects meeting the above definition based on investigator-assessed post-baseline responses. Similarly, analyses based on IRC responses will include subjects meeting the above definition based on IRC-assessed post-baseline responses. The efficacy-evaluable population may be used in supportive analyses of efficacy. Analyses of ORR and CBR will be also performed in the following analysis sets:

- All DLL3 High subjects in the efficacy-evaluable population
- All DLL3 Positive subjects in the efficacy-evaluable population

DOR and DOCB would be analyzed in the subsets of patients who achieved CR/PR and CR/PR/SD, respectively, in the above analysis sets.

The safety analysis population includes all subjects who receive any amount of study drug. A baseline measurement and at least one post-baseline laboratory or other safety-related measurement obtained after at least 1 dose of study treatment may be required for inclusion in the analysis of a specific safety parameter (e.g., lab shifts from baseline).

Pharmacokinetic analysis population consists of all subjects who receive at least 1 dose of study treatment and at least 1 post-baseline blood sample following a dose of study treatment. The pharmacokinetic data will be used in a population PK analysis that will be reported separately.

Retreatment analysis population consists of all subjects who receive at least 1 dose of study drug as retreatment. This population is defined for supplemental analyses. Selected efficacy outcomes (e.g., ORR and PFS) for such subjects during retreatment may be analyzed separately from the outcomes observed during the initial course of treatment. Adverse events reported during retreatment will be summarized separately from those observed during the initial course of treatment. Time to retreatment will also be summarized.

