Exploratory: 
• To explore relationship of DLL3 expression to clinical outcome during treatment with rovalpituzumab tesirine• To explore the efficacy and safety of rovalpituzumab tesirine retreatment when administered to subjects with DLL3-expressing SCLC who previously achieved clinical benefit on rovalpituzumab tesirine• To explore the effect of rovalpituzumab tesirine on disease biomarkers and pharmacodynamics	
TEST PRODUCTS, DOSE, AND MODE OF ADMINISTRATION:	

• Rovalpituzumab tesirine 0.3 mg/kg intravenously on Day 1 of each 6-week cycle for 2 cycles• Dexamethasone 8 mg orally (PO) twice daily on Day –1, Day 1 (the day of dosing), and Day 2 of each 6-week cycle	
STUDY DESIGN AND METHODOLOGY:	
This is an open-label, single-arm, Phase 2 study of rovalpituzumab tesirine in DLL3-expressing SCLC subjects with relapsed or refractory disease after receiving at least 2 previous regimens, including at least one platinum-based regimen. Only subjects with tumor cell expression that is DLL3 positive based on an immunohistochemistry (IHC) assay specification will be enrolled in the study. Enrollment will continue until up to approximately 123 DLL3 high, third-line subjects are treated. Enrollment will be carried out in two stages. In Stage 1, up to 60 evaluable, DLL3 high (per IHC assay specification), subjects may be enrolled. If among the 60 evaluable, DLL3 high (per IHC assay specification) subjects, more than 9 subjects achieve complete response or partial response, then enrollment will continue to Stage 2. At least 63 additional subjects that are DLL3 high (per IHC assay specification) will be enrolled in Stage 2. Otherwise enrollment will terminate. Of the enrolled DLL3 positive subjects, less than or equal to 30% can be fourth-line or later.	

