5.2 Efficacy Analysis by Line of Therapy

Efficacy analyses will include analysis by current line of therapy (3rd line and ≥3rd line) in the modified ITT population. Efficacy analyses by current line of therapy (3rd line and ≥3rd line) in the efficacy evaluable population will be included for all endpoints except for overall survival.

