7.4 Treatment Exposure and Compliance

Exposure to study treatment will be summarized and listed:

- Cumulative actual dose (mg)
- Treatment duration (cycles)

The number and percent of subjects with at least one dose modification (reduced, interrupted or delayed) will be summarized, which will include dose modification due to AE and other reasons. Dose modifications and study treatment discontinuation due to adverse events captured on AE CRF will be summarized in separate adverse event tables.

7.5 *Analysis of Primary Efficacy Endpoint*

All analyses of primary efficacy endpoints will be summarized for the modified ITT and efficacy evaluable populations defined in Section 5.

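### The efficacy-evaluable set drops unscanned subjects unless they died early of progression, which inflates supportive ORR and CBR; the SAP also disagrees with itself on whether OS belongs in that set

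*SAP*

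**What the plan says.** SAP 5.1 makes modified ITT, meaning everyone who received any study drug, the primary efficacy population. It adds an efficacy-evaluable set for optional supportive use: subjects with at least one post-baseline response assessment, plus "those that did not have a post-baseline response assessment and died within 42 days due to underlying disease progression". For this set it names ORR and CBR, with DOR and duration of clinical benefit in the matching subsets. OS is not named.

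The lead-in to SAP 7.5 is broader: "All analyses of primary efficacy endpoints will be summarized for the modified ITT and efficacy evaluable populations". SAP 4.3 lists OS as a primary endpoint. SAP 5.2, on analyses by line of therapy, says that efficacy-evaluable results "will be included for all endpoints except for overall survival".

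SAP 7.5.1 handles unscanned subjects without regard to cause. Anyone who dies before the first post-baseline lesion assessment is classed as Early Death, anyone who leaves the study before a scan is Indeterminate, and anyone without CR or PR is a non-responder. The analysis sets in Protocol 9.2.1.6 contain no efficacy-evaluable set; it is a SAP addition.

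**The concern.** Two subjects who die on the same day before any scan are treated differently. If the death is attributed to progression, the subject stays in the denominator; if it is attributed to toxicity or another cause, the subject is removed. Both are treatment failures. Membership therefore depends on an outcome after dosing and on a judgement about its cause, in an open-label trial. Neither document describes adjudication of cause of death.

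That judgement may be hard here. Protocol 5.5.1 describes potentially life-threatening effusions on treatment and lists progression among the alternative causes to rule out. Protocol 7.6.1.2 gives malignant pleural effusion as an example of how progression may be reported.

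At stake is whether the supportive ORR and CBR can be read as independent support for the primary result when they can only equal or exceed it. For OS, the question is whether a programmer following 7.5 would produce survival estimates in a set that is partly defined by having lived long enough to be scanned.

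**Working it through.** **The plan's own design.** Inputs from the protocol synopsis:
- null rate 15%: "A response rate of 15% or less is typically observed in this advanced state of the disease"
- alternative 25%: "It is assumed that at least 25% of subjects treated with rovalpituzumab tesirine will achieve complete or partial response"
- operating characteristics: "80% power at a one-side significance level of 0.025"
- Stage 1: "In Stage 1, up to 60 evaluable, DLL3 high (per IHC assay specification), subjects may be enrolled"
- continuation rule: "more than 9 subjects achieve complete response or partial response, then enrollment will continue to Stage 2"
- Stage 2: 63 more, total 123, Simon minimax.

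P(success) = Σ over x > 9 of Bin(x; 60, p) × P(Bin(63, p) > r − x). The final cut r is not in the readable text. A search over total n from 110 upward finds 123 as the smallest feasible total. At 123 the lowest expected sample size is at n1 = 60, r1 = 9, r = 26, with alpha 0.0242 and power 0.8001. The stated design reproduces, with success at 27 or more responders. This rule is a count of responders, so removing non-responders from a supportive denominator cannot change it. The Stage 1 rule also uses its own definition of evaluable (Protocol 9.2.10, SAP 8), not the one in SAP 5.1.

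**ORR and CBR.** Let N be treated subjects, x responders and k excluded subjects. An excluded subject has no assessment and cannot be CR, PR or SD, so x is unchanged:

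evaluable rate = x/(N − k) = (x/N)/(1 − e), with e = k/N.

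The rate can never fall below modified ITT. The documents do not give k, so k = 6, 12 and 18 are assumed (e = 4.9%, 9.8%, 14.6%; factors 123/117 = 1.05, 123/111 = 1.11, 123/105 = 1.17). The responder counts are also assumed: 18 and 31 are about 15% and 25% of 123, and 25 lies between. Cells show ORR and the exact 95% lower bound.

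| Responders | k = 0 (123) | k = 6 (117) | k = 12 (111) | k = 18 (105) |
|---|---|---|---|---|
| 18 | 14.6% (8.9%) | 15.4% (9.4%) | 16.2% (9.9%) | 17.1% (10.5%) |
| 25 | 20.3% (13.6%) | 21.4% (14.3%) | 22.5% (15.1%) | 23.8% (16.0%) |
| 31 | 25.2% (17.8%) | 26.5% (18.8%) | 27.9% (19.8%) | 29.5% (21.0%) |

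With 25 responders and 12 or 18 exclusions, the lower bound exceeds 15% only in the efficacy-evaluable set. With 18 or 31 responders both sets fall on the same side. Here k counts every unscanned exclusion, including living dropouts.

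**OS, only if 7.5 governs.** Assume exponential survival with a median of 4 to 6 months (Protocol 1.1.1 gives under 6 months for recurrent disease), and λ = ln 2/median. Deaths within 42 days: 1 − exp(−λ × 42/30.44) = 21.3%, 17.4% and 14.7% for medians of 4, 5 and 6 months. Assume 25% to 50% of these are unscanned and not attributed to progression, and that no living subject is excluded. Then e runs from 0.25 × 14.7% = 3.7% to 0.50 × 21.3% = 10.6%. After day 42, S_evaluable(t) = S(t)/(1 − e), and the median becomes −ln[0.5(1 − e)]/λ. At a 5-month median:
- e = 4.4%: median 5.32 months; 6-month survival 43.5% becomes 45.5%
- e = 8.7%: median 5.66 months; 6-month survival 43.5% becomes 47.7%

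Across the range the median rises by about 0.3 to 0.7 months and 6-month survival by about 2 to 4 points. Excluding living dropouts could offset some of this.

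**The case against.** The strongest reply is that the primary analysis already does the right thing. Modified ITT keeps every treated subject, a toxic death before the first scan counts as a non-response, and 5.1 gives the evaluable set only an optional supportive role. SAP 7.1 reports the size of each population, and deaths and fatal adverse events are reported on the full safety population. All of that stands, and it limits the point to supportive analyses. The clause also keeps some early deaths that the interim definition of evaluable would leave out, but that does not justify a cause-of-death condition.

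On OS, the 7.5 sentence itself refers back to Section 5, which names only ORR and CBR for this set. Appendix G lists one overall OS table and one OS table by 3L and 3L+, whereas DOR, duration of clinical benefit and PFS each have two by-line tables. This suggests that efficacy-evaluable OS may not be intended. It is not proof, because table subtitles may be missing, and the 5.2 exclusion covers by-line analyses only. The conflict in wording remains.

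A reader might infer that the shift rivals the distance between the null and the success cut. It does not: 27/123 = 22.0% lies 7.0 points above 15%, against shifts of 1.0, 2.2 and 3.5 points in the 25-responder example. Nor does the whole shift come from the cause-of-death condition, since the example also drops living dropouts, whom a change to the death clause would not restore.

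**Conclusion.** The point holds for supportive ORR and CBR. The upward direction relative to modified ITT is arithmetic whenever anyone is excluded. The size is 1/(1−e), and e is not in the documents. With an assumed 25 responders of 123, exclusions of 6 to 18 add 1.0 to 3.5 points to ORR; this is an upper limit on what the death-only edit would recover. The crossing of 15% by the lower bound depends on the assumed responder count and is not a general result.

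The documents do not support reading this as a bias in the primary ORR, the primary OS or the Simon decision. Nor do they support stating as fact that the plan yields an upward-biased OS. What they show is that 7.5 goes beyond 5.1 and conflicts with 5.2. If 7.5 governs, upward bias is probable, because the set is partly conditioned on surviving to a scan. It is not certain, because unscanned living subjects, whose survival may be longer or unknown, leave the set while early progression deaths stay. The OS figures rest on exponential survival and an assumed share of early deaths not attributed to progression.

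**What to change.** - **SAP 5.1:** replace the early-death clause with death from any cause before a first post-baseline assessment, counted as a non-response. This matches the Early Death category in 7.5.1 and removes both the cause condition and the 42-day limit. Living dropouts would still be excluded; keeping them too would make the set identical to modified ITT.
- **Reporting:** give the number excluded from the efficacy-evaluable set by reason (for example, living with no scan), separately for the IRC and investigator versions.
- **SAP 7.5:** state that OS is analysed in modified ITT only. Efficacy-evaluable ORR and CBR may remain, as 5.1 provides.

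The cost is a few text edits and one added breakdown, with no new data and no change to the primary analysis. The downside is slightly lower supportive ORR and CBR.
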